-Plasma metabolomics, biomarkers, hormones	Blood draw
-Dates of hospitalization and operation	Medical records
-Daily laboratory results (e.g. blood glucose, creatinine, eGFR)	Medical records
-Treatment (IV or SC insulin dosage, use of corticosteroids)	Medical records
-Complications and adverse events (defined below)	Self-report and medical records
-Length of ICU and hospital stay	Medical records

Data Collection on Complications

- Surgical wound infection (superficial and deep sternal wound infection).
- Pneumonia (CDC criteria).
- Acute kidney injury defined as an increment in serum creatinine ≥ 0.3 mg/dL from baseline or ≥ 1.5 times baseline creatinine (KDIGO)
- Acute myocardial infarction (AMI): (1) typical increase and gradual decrease (troponin) or (2) more rapid increase and decrease (creatinine kinase MB) of biochemical markers of myocardial necrosis with at least one of the following: (a) ischemic symptoms, (b) development of pathologic Q waves on the electrocardiogram, (c) electrocardiographic changes indicative of ischemia (ST-segment elevation or depression), or (d) coronary artery intervention (e.g., coronary angioplasty).

- **Clinical Management Guidelines:** The primary care team will provide care regarding the use of vasopressors, ventilator support, sedation, antibiotics, and treatment of co-morbid conditions.
 - a. Assessment and monitoring of BG concentration. Information on BG measurements both at bedside by glucose meter and by hospital laboratory will be collected. BG will be measured every 1-2 hour during continuous insulin infusion (CII) in the ICU, and before meals and at bedtime after transition to regular wards. Hypoglycemia is the main adverse event and safety concern in the study. The number of mild (≤ 70 mg/dL) and severe hypoglycemia (≤ 40 mg/dL) and clinical consequences (neurological and cardiovascular) will be compared between groups.
 - b. Assessment and monitoring of hospital mortality. Investigators will follow study subjects daily and the date and presumed cause of death will be recorded. Information on the attending physician's summary of events surrounding subject's demise will also be documented.
 - c. Assessment and monitoring of wound infections. The investigators will review each subject's records daily from Monday to Friday regarding potential new infections. Data from the weekends will be collected the following Monday. Definitions: Deep Sternal Wound Infection (DSWI): chest wound infection involving the sternum or mediastinal tissues, including mediastinitis; Superficial Sternal Wound Infection (SSWI) (not involving the sternal bone or wires): chest wound infections involving the skin or subcutaneous tissues, or both.
 - d. Assessment and monitoring of nosocomial infections. The following daily information will be collected for nosocomial infection surveillance: 1) temperature curve; 2) white blood cell counts; 3) daily progress notes; 4) daily clinical microbiology laboratory data; 5) all relevant radiographic reports; 6) orders for antimicrobial agents; 7) communication, as needed, with primary physicians and site infectious disease consultants; 8) use of the CDC guidelines for diagnosis of specific nosocomial infections.
 - e. Assessment and monitoring of days on mechanical ventilation. The need for mechanical ventilation will be monitored daily. The day the subject is weaned from the ventilator will be recorded.
 - f. Assessment and monitoring of length of SICU and hospital stay. The morning location of the study subject (in either the SICU or surgical ward) and date of hospital discharge will be recorded daily.
 - g. Assessment and monitoring of renal function. Acute kidney injury - new-onset abnormal renal function is defined as an increment of creatinine level above 50% from baseline.
 - h. Cerebrovascular accident (CVA). Defined as central neurologic deficit persisting more than 72 hours (permanent stroke), transient ischemic attack, deficit resolving within 24 hours, or deficit lasting more than 24 hours but less than 72 hours (reversible ischemic neurologic deficit).
- Data collection and data entry. Study members will enter baseline and daily data for this study into data collection paper forms and into an electronic database provided by the Emory Research Information Technology Department. Baseline data will include demographics/history form (subject gender, date of birth, ethnicity, dates of hospitalization and operation, history of diabetes, and comorbid conditions, body weight, BMI, smoking status, type of surgery, APACHE score. Daily information will be collected on treatment (insulin IV or SC and dosage, antibiotics, use of corticosteroids), nutrition support, BG and laboratory values, hospital complications and adverse events, and length of ICU and hospital stay.

E.1.3. Potential Risks

- **Potential Risks/Discomforts:**
 - a. Venipuncture: There is some minor discomfort and risk of mild bruising during venipuncture. Standard sterile techniques will be used during phlebotomy; thus, infection is unlikely. Disposable pre-sterilized needles and syringes will be used for all blood drawing in this study; needles and syringes will not be reused. Discomforts associated with venipuncture are rapidly reversible. Approximately 40 mL of blood will be obtained for all the blood measurements proposed.

- b. Hypoglycemia: In our previous ICU studies, we observed that <10% of cardiac surgery subjects during CII and 20-30% during SC insulin experienced hypoglycemia. No episodes of severe hypoglycemia were observed during CII in our study. The use of insulin in combination with GLP1-RA may increase the risk of hypoglycemia. The number of mild (≤ 70 mg/dL) and severe hypoglycemia (≤ 40 mg/dL) and clinical consequences (neurological and cardiovascular) will be compared between groups. Treatment of hypoglycemia: hypoglycemia, defined as a BG <70 mg/dL will be treated by a standard hypoglycemia protocol available at each hospital.
- c. Hyperglycemia: it is very likely that a high proportion of patients randomized to placebo develop hyperglycemia. All subjects with hyperglycemia (in both groups) will be treated by standard protocols in the ICU units at each hospital. We expect that ~50-60% of subjects randomized to placebo will experience one or more episodes of hyperglycemia. The frequency of severe hyperglycemia will be analyzed statistically.
- d. Gastrointestinal adverse effects: include nausea and vomiting, which are more common in patients treated with dulaglutide compared to placebo. The frequency of nausea and vomiting is reported in up to 10% of patients receiving dulaglutide in combination to oral agents compared to 3.5% in patients receiving placebo plus oral agents. If a participant developed nausea during hospitalization the research team will perform a phone call visit on post-discharge day 2 to ensure safety. There have been few reported events of acute pancreatitis with the use of GLP1-RA (typically reported among patients at higher risk of pancreatitis). Subjects should be informed of the characteristic symptoms of acute pancreatitis: persistent, severe abdominal pain. If pancreatitis is suspected, potentially suspect medicinal products should be discontinued. Patient will receive a single 0.75mg dose of dulaglutide. If the investigator suspects acute pancreatitis, all suspected drugs should be discontinued until confirmatory test have been conducted and appropriate treatment should be initiated. Subjects diagnosed with acute pancreatitis (as a minimum 2 of 3: characteristic abdominal pain, amylase and/or lipase >3 xUNR or characteristic findings on CT scan/ MRI) should be withdrawn from the study.

- **Alternative treatments:** The alternative is for a participant to not participate in the trial.

E.1.4 Adequacy of Protection Against Risks

a. Recruitment and Informed Consent

- **Recruitment and Informed consent:** Potential study subjects will be identified and pre-screened among patients undergoing CABG surgery at Emory affiliated hospitals.
- [name] or the study coordinator will conduct informed consent in eligible subjects prior to any study procedures. Screening and recruitment reports will be generated monthly that include actual and expected recruitment statistics.
- **Description of informed consent process:** A written and signed informed consent will be obtained in person in a private area. After identification of a person as potentially eligible for the study, approved study personnel will explain the study in detail in the consent form as well as verbally. Potential participants will be informed of the purpose of the study, the study protocol, and the routine and potential risks associated with the study procedures. All risks, costs, and benefits will be discussed. Participants will be assured of their right to withdraw at any time without prejudice to their care. They will be assured of confidentiality in maintaining records and reporting of results. A separate consent will also be obtained for permission to store biological samples for future studies. Any additional information regarding questions or concerns from potential or confirmed study participants will be provided. Participants will have ample time to call the study team with questions/concerns and make an informed decision about their participation in the study.

An Institutional Review Board (IRB) approved study designee will provide verbal and written consent. The study is discussed thoroughly with each potential participant, and he/she will be encouraged to ask questions regarding the study and her participation. If the potential participant decides to enroll, he/she will sign the written informed consent, as will the study team member conducting informed consent. A copy of the signed consent form will be provided to enrolled study participants. The

consent process will be documented using a template provided by the Emory IRB in the "Consent Clinical Trial Tools" section of the Emory IRB website.

Subjects must be able to read, write and understand the consent documents. Study personnel will subjectively assess the capacity to give informed consent through the use of questions to ensure understanding and comprehension of the study. Only adults will participate in this study.

- **Waivers:** We will request a partial HIPAA waiver to be able to access medical records for screening.
- b. ***Protections Against Risk***

- **Protections against risks:** Adverse events are expected to be uncommon and not pose more than minimal risk to the study participants.

- Subject identification and screening for eligibility: Our strict inclusion and exclusion criteria for entry (outlined above) will help to minimize potential risks. All subjects will be monitored closely by frequent clinical assessments and review of safety laboratory tests by experienced clinicians. In addition, we will carefully monitor capillary BG at the bedside using the hospital certified meter, b) only experienced nurses/or phlebotomist will draw blood samples, c) patients will be closely monitored in the ICU, d) no patients with history of significant pancreatic, renal or hepatic failure will be recruited in this study.
- Blood sampling: Experienced research nurses will use aseptic techniques for all study blood draws. Participants will be asked to stay hydrated with water the day before the study visit. Universal precautions will be employed in all instances involving human specimens and all blood processed under at least BSL2 conditions. Discomforts associated with venipuncture are rapidly reversible. During surgery trained personnel will collect the blood samples.
- Hyperglycemia: All patients that develop hyperglycemia will be treated by standard insulin protocols in the ICU and non-ICU units available at each hospital.
- Hypoglycemia: In our previous ICU studies, we observed that <10% of cardiac surgery subjects during CII and 20-30% during SC insulin experienced hypoglycemia. No single episode of severe hypoglycemia was observed during CII in our study in CABG patients. The use of insulin in combination with GLP1-RA may increase the risk of hypoglycemia. The number of mild (≤ 70 mg/dL) and severe hypoglycemia (≤ 40 mg/dL) and clinical consequences (neurological and cardiovascular) will be compared between groups. Any episode of hypoglycemia (BG < 70 mg/dL) will be treated by a standard hypoglycemia protocol available at each hospital.
- Privacy/Confidentiality: The subjects' extracted medical records and data from the study will be initially stored on paper prior to transfer to electronic format. The encrypted electronic record will remain on the principal investigator's password protected computer in his locked office. Confidentiality will be assured by the use of subject codes rather than personal identifiers. The master list connecting the subject codes to identifying information will be secured in the Emory's computerized database. All paper subject records will be kept in locked file cabinets in the PI's research office and will be accessible only to the PI and the investigative team. Only institutional review board (IRB)-approved study personnel will have access to individually identifiable information about human subjects. This may include the study PI, co-investigators, research coordinators, and other approved study personnel. All information and materials will be obtained for research purposes only and the data will be kept in strict confidence for use in this proposed research only.
- Other: Since the proposed tests are not inherently hazardous, hazard is likely to occur only as the result of impaired participant confidence or sudden unwillingness to complete a test. To avoid this possibility, study personnel will thoroughly explain all tests to potential participants prior to them signing the consent form. Potential participants will have the opportunity to see all test equipment and facilities before giving consent or undergoing testing. Every effort will be taken to prevent injury or distress that may result from this

- study. [name], or a study physician will be on call for support. A qualified physician will have primary responsibility for inpatient care.
- Data and Safety Monitoring: A senior faculty Safety Officer, with expertise in randomized controlled clinical trials will be designated as the Safety Officer for this study. He/she will review semi-annual reports created by [name] and make recommendations regarding the continuation of study. [name] will review this protocol on a continuing basis for subject safety and include the results of the review in semi-annual reports to the Safety Officer and annual progress reports submitted to the IRB. A full Data and Safety Monitoring Plan (DSMP) is provided in a separate document.
- **Medical intervention:** If a participant suffers from distress during a procedure, the procedure will be discontinued. The participant will then be managed in the Emory affiliated Hospital surgical suite or in the CRN unit, which, if applicable or warranted, have immediate access to EKG monitoring, cardiac resuscitation equipment and are located in close proximity to Emergency Departments.
- Every effort will be taken to prevent injury or distress that may result from this study. A study physician will be on call for support. A qualified physician will have primary responsibility for inpatient care.

E.1.5 Potential Benefits of the Proposed Research to Human Subjects and Others

- **Potential Benefits:** There may be no specific health benefit to patients' participation in the study. However, participants will receive information on their blood glucose levels during the hospital stay, which they may use to inform their own health decisions/activities.
- **Risk/Benefit Assessment:** The risks incurred are minimal relative to the potential benefit of gaining information about individuals' health. Our group has extensive experience in glycemic control in the hospital and we will follow closely all patients for timely and appropriate management of hyperglycemia and hypoglycemia.

E.1.6. Importance of the Knowledge to be Gained

- **Importance of Knowledge:** The long-term goal of this study is to identify underlying mechanisms that lead to hyperglycemia and their association with established biomarkers known to predict risk of death in patients with coronary disease. This study has the potential to identify clinically meaningful metabolites to guide the development of important biomarkers (to be assessed in independent cohort studies) that can help to stratify patients at risk for hospital complications. The findings that arise from this research will also inform scientists in developing new technologies and designing future therapies to better understand and treat metabolic derangement during acute stress. We also aim to prevent hyperglycemia with an agent associated with lower risk of iatrogenic hypoglycemia. If our hypothesis is correct, such information could guide future clinical trials aimed at preventing hyperglycemia with the goal of impacting meaningful endpoints (cost, hospital complications, and mortality).
- **Risk/Importance Assessment:** The anticipated benefits of the proposed research study outweigh the potential risks to participating subjects. The potential for serious adverse effects is small and the potential benefit to society is high enough for the studies to proceed.

E.1.7 Data and Safety Monitoring Plan (DSMP): Please see DSMP provided as a separate document.

E.1.8 ClinicalTrials.gov Requirement: This clinical trial will be registered on ClinicalTrials.gov. Final results will be published on this site.

E.1.9 Statistical Considerations

Sample Size Calculation and Power Analysis: with a Wilcoxon test, for an effect size >1 at alpha=0.05 and power=0.80, the proposed sample size of N=50 for this experiment will be more than adequate for the main objective of identifying differentially expressed metabolites and pathways in Aim 1, as shown in previous studies.^{134,138} For Aim 2 we assumed N=60. No preliminary data on prevention of hyperglycemia is available. Assuming an effect size of ~0.50 on hyperglycemia prevention with χ^2 goodness of fit for contingency tables, power 80%, alpha=0.05, a total of 52 patients would be needed. In our previous RCT (GLUCO-CABG⁴) non-DM patients in the conservative group had a mean BG 143mg/dl vs. 127mg/dl in the intensive group. This difference was associated with a lower composite score of complications in the intensive group. It is reasonable to assume the standard deviation of the mean BG is bounded around 40 mg/dl. With two-sample t tests or Wilcoxon tests, alpha=0.05, 25 subjects for each arm would be needed to ensure 80% power to reject the hypothesis that the mean BG in patients treated with dulaglutide is not 16 mg/dl lower compared to placebo. Accounting for ~15% attrition rate this leads to a final total sample size estimate of 60 patients for both considerations. This study is not powered to assess differences in hospital complications between groups.

Research Timeline	Yr1	Yr2	Yr3	Yr4	Yr5
Aim 1. Case-Control					
Study initiation (IRB)	x				
Recruitment / sample collection	xx	xx	xxx	xx	
Lab assays / data processing				xxx	xxx
Analysis / manuscript preparation				xxx	xxx
Aim 2. Clinical Trial					
Study initiation (IRB)	x				
Randomization / sample collection	xx	xxx	xx	xx	
Lab assays / data processing				xxx	xxx
Analysis / manuscript preparation				xxx	xxx

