Protein Metabolism	BCAA (Isoleucine, leucine, valine) Aromatic Acids (tyrosine, phenylalanine) Other: glycine, glutamine/glutamate ratio	Meta-analyses of multiple cohorts show that BCAA, AAA increase the risk of chronic hyperglycemia. Some AA are protective (glycine, glutamine/glutamate ratio) ³⁷⁻⁴⁷ . BCAA lead to mTOR/S6K1 kinase pathway activation and serine phosphorylation of IRS1 leading to insulin resistance. BCAA catabolic flux can lead to glutamate transamination to alanine and increased gluconeogenesis, as well as insulin secretion defects. ⁴⁸⁻⁵⁰ BCAA are also associated with CVD. ⁴² The product of valine catabolism, 3-HIB has emerged as a potential mediator linking BCAA to regulation of fatty acid flux and insulin resistance (IR). ^{51,52} We observed higher abundance of 3-HIB in subjects with hyperglycemic crises and delayed response to insulin suggesting IR. Recently, 3-HIB was associated with incident diabetes. ⁵³
Lipid Metabolism	Acylcarnitines, ceramides / sphingosine, triacylglycerols (TAGs),	Elevated medium chain acylcarnitines lead to pancreatic β-cell dysfunction. ⁴⁰ Ceramides, and acylcarnitines are associated with insulin resistance and incident CVD ^{41,44-46,54,55} . Sphingosine, a ceramide derivate is elevated in prolonged ketoacidosis, and is associated with insulin resistance. ⁵⁶
Carbohydrate Metabolism	Glucose, Insulin	Hyperglycemia can lead to inflammation, oxidative stress, and a pro-thrombotic state ³²⁻³⁶ . HOMA-IR and HOMA-B are well-described surrogates of insulin resistance and insulin secretion derived from insulin and glucose levels.

Hormonal response	Cortisol, glucagon	Counterregulatory hormones are expected to increase during cardiovascular surgery (GLUCO CABG) ^{3,4}
Inflammatory pathways	TNF-a, IL-6, CRP	TNF-a, IL-6 are inflammatory markers known to cause insulin resistance (TNF-a, IL-6) and insulin secretion defects ⁵⁷⁻⁶² and associated with cardiovascular risk. Inflammatory cytokine concentrations are acutely increased by hyperglycemia in humans. ³⁶ Levels of inflammatory markers are increased for days after CABG surgery. ³ CRP is an established CVD risk factor. ⁶³
Cell stress	Heat shock protein (HSP)	Hyperglycaemia upregulates HSP60 & HSP70. ⁶⁴ HSP70 is associated with incident CVD. ^{2,65,66} ([name])
Immune pathways	suPAR	SuPAR is a marker of immune activation associated with all-cause death and myocardial infarction in patients with CVD.

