1) The underlying mechanisms leading to stress hyperglycemia and poor hospital outcome are not well understood. It is unknown if hyperglycemia is a mediator in the development of hospital complications, or a bystander marker only representing severity of disease. Serial assessments of relevant candidate metabolites and biomarkers before and after the acute stress episode will facilitate our understanding of potential mediators of stress hyperglycemia and the metabolic response to stress. CABG surgery represents a unique human model to study in depth these relationships.

2) Metabolomics (HRM) is an emerging scientific field that enables profiling of thousands of metabolites to provide a functional readout of cellular metabolism in plasma and other bio samples. The use of metabolomics can identify metabolites and metabolic pathways implicated in the development of stress hyperglycemia. We expect to find an association of metabolites derived from protein and fatty acid catabolism (such as BCAA, and specifically 3-HIB) with stress hyperglycemia. In addition, serial assessments of glucose levels, candidate metabolites and biomarkers as well as an integrative network analysis to find multilevel associations between them will facilitate for the first time an approximation to causality interpretations. No previous studies have applied metabolomics analysis to understand stress-hyperglycemia. Novel bioinformatics tools such as metabolome-wide association studies (xMWAS) have the capability to facilitate an integrative network analysis to find multilevel associations and identify metabolic pathways and network structures in association with stress-hyperglycemia.

3) We will examine biomarkers associated with meaningful cardiovascular disease outcomes that represent inflammation (C-reactive protein), coagulation (fibrin degradation products), cell stress (heat shock protein-70), and immune activation (suPAR). Hyperglycemia can lead to activation of these pathways. This study will for the first time examine longitudinally the relationship between clinically relevant biomarkers and stress-hyperglycemia in patients with established cardiovascular disease.

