General overview: The proposed research will test in a nested case-control study associations of individual metabolites and broader metabolomics profiles as well as counter-regulatory hormones and biomarkers with stress-hyperglycemia (Aim 1). For this analysis patients will be stratified according to the outcome of stress-hyperglycemia (cases) and compared to controls (no hyperglycemia). For Aim 2 a randomized clinical trial will be conducted to examine the effects of exposure to dulaglutide on the prevention of stress-hyperglycemia and the metabolic inflammatory response in the perioperative period, (Fig. 6).

[figure not shown]

Figure 6. General overview. Aim 1 will be tested with a case-control study design. In Aim 2 we will conduct a clinical trial.

Specific Aims

D1. Case – control study

Aim 1. To examine baseline and postoperative metabolic profiles of non-diabetic CABG patients with stress hyperglycemia.

Rationale: the underlying mechanisms leading to stress-hyperglycemia and its association with poor outcomes in cardiac surgery patients are not well understood. We aim to study metabolic signatures associated with hyperglycemia and path-specific biomarkers. We will test the temporal relationships between candidate metabolites/pathways (Table 1) and specific biomarkers with stress-hyperglycemia.

Study design: In a nested case-control study (N=50) we will compare the characteristics of patients developing postoperative stress-hyperglycemia (cases) compared to patients that do not develop stress-hyperglycemia (age-matched controls). A proportion of patients will be derived from the placebo arm of the randomized trial. This design will allow efficient recruitment from our cohort of CABG patients to allow substantial savings in cost

and time. **Case definition:** stress-hyperglycemia is defined as a BG >140mg/dl on arrival to the ICU. Please see additional details in Human Subjects section.

Study Population: we will include patients with ages between 18-80 years without a history of diabetes [BG \leq 125 mg/dl and HbA1c <6.5%] undergoing CABG surgery. Patients will be recruited from three academic hospitals, including Emory University Hospital, Emory Hospital Midtown (EUHM), and Grady M Hospital in Atlanta, GA. [name] (Chief of Division and Director of the CTS Center for Clinical Research) is a key collaborator and will facilitate recruitment and perform CABG surgeries.

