Aim 1.1 Targeted Approach: We will determine cross-sectional and longitudinal changes of ceramides, acylcarnitines, BCAA, and a biomarker panel for CVD outcomes and their relationship with stress hyperglycemia (BG >140mg/dl on ICU arrival). Path-specific biomarkers include: TNF- α and C-reactive protein (inflammation), fibrin degradation products (pro-thrombosis), heat shock protein-70 (cell stress), and suPAR (immune modulation and inflammation). Counterregulatory hormones include: cortisol, glucagon. Glucose, insulin and indexes of insulin sensitivity/insulin resistance: will be derived from glucose, insulin and c-peptide values. **Methods:** Plasma samples will be stored at -80°C until analysis. Serum CRP and FDP including fragments D and E, D -dimer, and additional intermediate cleavage products will be determined (FirstMark, San Diego, CA). Serum HSP-70 will be measured with a sandwich enzyme-linked immunosorbent assay (R&D Systems, Minneapolis, MN). Plasma suPAR levels will be measured using commercially available kits (suPARnostic kit; Virogates, Copenhagen, Denmark). Minimum detectable CRP, FDP, HSP-70, and suPAR have been reported at 0.1 mg/L, 0.06 $\mu\text{g}/\text{mL}$, 0.313 ng/ml, and 0.1 ng/ml, as described previously.⁶⁵⁻⁶⁸ Liquid chromatography tandem mass spectrometry techniques will be used to quantitatively profile ceramides, acylcarnitines, branched chain amino acids (leucine, isoleucine, valine), and aromatic amino acids (tyrosine and phenylalanine) in plasma samples along with standard reference samples. Glucose levels will be analyzed by the hexokinase method (Beckman-Coulter, Los Angeles, CA). Counterregulatory hormones, insulin, C-peptide levels by two-site sequential chemiluminescent immunometric assays. Surrogates of beta cell function (HOMA-B) and insulin resistance (HOMA-IR) will be derived from fasting glucose, c-peptide and insulin.

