With advanced data extraction provided by xMSanalyzer and apLCMS, I will be able to also measure a spectrum of high and low abundance metabolites. We will utilize a well-established computational metabolomics workflow with rigorous standard operating procedures outlined in Fig. 7.¹²⁴ Data Selection and Annotation (Biostatistics and Bioinformatics Tools): HRM data will be processed using apLCMS with xMSanalyzer^{125,126}. Feature annotation will be performed using xMSannotator.¹²⁷ xMSannotator provides confidence scores for more than 2,000 metabolites, with more than 300 metabolites having confirmed identities and including most major pathways. The quality of data will be judged based on established rigorous criteria (e.g. coefficient of variation within replicates and QC samples, the percentage of missing values, the percentage of data exceeding detection limits of the machinery, batch-effects, and the percentage of outliers, etc.). Principal Component Analysis (PCA) will be used for batch-effect evaluation and ComBat¹²² will be used for batch- effect correction if necessary. Identifying expressed metabolites across different time points: we will use univariate and multivariate statistical methods, such as linear mixed effects models with post-hoc Tukey tests, LIMMA, and multilevel sparse Partial Least Squares Discriminant Analysis (msPLSDA).^{128,129} Multiple hypotheses testing correction will be performed using the Benjamini-Hochberg method.¹³⁰ Identifying putative biomarkers: we will use a consensus feature selection approach such that metabolic signatures identified by both univariate and multivariate approaches will be used for downstream analyses. K-fold and leave-one-out cross-validation using Support Vector Machine (SVM) will be performed to evaluate predictive accuracy of putative biomarkers. Two-way hierarchical clustering analysis will be performed to identify clusters of correlated metabolic features and to evaluate the ability of the discriminatory features to separate samples based on stress-hyperglycemia. Pathway enrichment analysis: Pathway analysis will be performed with pathway enrichment software for untargeted metabolomics data (Mummichog and MetabNet)^{131,132}. Where appropriate, additional chemical verification will be performed for significant metabolites of interest according to retention time and characteristic ion dissociation (MS/MS) patterns relative to authentic standards. Metabolome-wide association study (MWAS) of specific metabolites will be conducted (MetabNet) to facilitate detection of their related metabolic pathways and network structures in association with glucose levels (continuous) and stress-hyperglycemia as a discrete dichotomous variable.

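### Several metabolites that the plan names as candidates, and the 3-HIB it singles out, are missing from the targeted panel; as written, their only individual test is inside the untargeted screen.

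*Combined protocol and SAP*

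**What the plan says.** **What is to be tested.** The Rationale in section D1 states: "We will test the temporal relationships between candidate metabolites/pathways (Table 1) and specific biomarkers with stress-hyperglycemia". In Table 1 the candidate column for protein metabolism includes "Other: glycine, glutamine/glutamate ratio", and the lipid row reads "Acylcarnitines, ceramides / sphingosine, triacylglycerols (TAGs". 3-HIB is in the rationale column of the same table, where it "has emerged as a potential mediator linking BCAA to regulation of fatty acid flux and insulin resistance (IR". Section B, item 2 expects an association for catabolic products "such as BCAA, and specifically 3-HIB) with stress hyperglycemia". Sections C.6 and C.7 report 3-HIB and sphingosine as signals in the team's own ketoacidosis data.

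**What the targeted assay measures.** The Methods of Aim 1.1 say that LC-MS/MS will "quantitatively profile ceramides, acylcarnitines, branched chain amino acids (leucine, isoleucine, valine), and aromatic amino acids (tyrosine and phenylalanine) in plasma samples". No other targeted assay for metabolites of this kind is described.

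**What the untargeted arm does.** Aim 1.2 applies Benjamini-Hochberg without stating the FDR level. Section E.1.2 puts the screen at more than 2,000 metabolites. Where judged appropriate, "additional chemical verification will be performed for significant metabolites of interest". The Figure 7 caption adds reference standardization for quantifying metabolites of interest. Aim 2.3 reuses the Aim 1 procedures.

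**The concern.** A metabolite named in advance would normally be tested on its own or in a short list. Here some named candidates are in the targeted panel and others are not, and the plan does not explain the split. Those left out compete with the whole feature list, so they face a much stricter threshold. The sample size argument in section E.1.9 uses alpha 0.05 for one test and makes no allowance for that.

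The cost falls mainly on null results. If a candidate misses the screen's threshold, the plan does not require its feature to be confirmed against a standard. The team could not then tell an absent association from low power or an uncertain annotation. The same gap passes to the dulaglutide v placebo comparison in Aim 2.3.

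**Working it through.** **Inputs from the plan.** Section E.1.9: "with a Wilcoxon test, for an effect size >1 at alpha=0.05 and power=0.80, the proposed sample size of N=50 for this experiment". Section E.1.1 gives 25 controls, hence 25 cases of 50. The screen exceeds 2,000 metabolites (E.1.2). The preliminary data had 216 significant features of 4,144 (C.6), or 216/4,144 = 5.2%.

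**Assumptions.** Two-sided tests, normal data, independent features, matching ignored, and a difference of exactly 1 SD. FDR is taken as 0.05, with 0.20 shown as a range because the plan gives no level.

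**Step 1: the plan's own figure.** Power = 1 − F(t\*; df, δ√(n/2)), where F is the noncentral t distribution and t\* its two-sided critical value. For the Wilcoxon test n is replaced by n × 3/π. With n = 25, n × 3/π = 23.87, the noncentrality is √(23.87/2) = 3.45, and power is 0.92. Simulation also gives 0.92. The smallest n with 80% power is 18 per group (total 36). The plan's statement that N=50 is more than adequate is therefore correct for one test at 0.05.

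**Step 2: the threshold in the screen.** With m features, FDR level q and R features declared, Benjamini-Hochberg declares those with p ≤ qR/m. For m = 2,000 and q = 0.05:

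- R = 100: 0.05 × 100/2,000 = 0.0025, power 0.58
- R = 20: 0.0005, power 0.36
- R = 5: 0.000125, power 0.21

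**Step 3: simulated Benjamini-Hochberg, average power per true signal.**

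| Setting | FDR 0.05 | FDR 0.20 |
|---|---|---|
| Five-member family, 1–3 true signals | 0.77–0.87 | – |
| 2,000 features, 20 true | 0.19–0.20 | 0.48–0.49 |
| 2,000 features, 50 true | 0.35 | 0.64 |
| 2,000 features, 100 true | 0.48 | 0.76 |
| 2,000 features, 200 true | 0.61 | 0.84 |
| 4,144 features, 216 true | 0.49 | 0.76 |
| Assumed targeted panel of 30–100 analytes, 1–10 true | 0.52–0.71 | – |

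Repeat runs differ by about 0.01–0.02. The five members are 3-HIB, sphingosine, glycine, glutamine and glutamate. If the ratio is tested as a sixth, the strictest step is 0.05/6, where power is 0.74. The last row shows that placing the omitted metabolites in a large panel corrected as a whole recovers less than a small separate family does.

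**The case against.** **Standing of 3-HIB.** A reader might infer that the plan leaves its most specific Aim 1 hypothesis out of the panel. The documents do not support that. The stated hypotheses name ceramides, acylcarnitines and BCAAs, and all three are in the panel. 3-HIB is an example in section B and a rationale entry in Table 1. Sphingosine shares a Table 1 entry with ceramides and may be meant to fall under them. The Aim 1.2 hypothesis also covers known candidates, so reading some of them from the untargeted data may be deliberate. These points stand, but they give the omitted candidates no test of their own.

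**Identity.** A reader might infer that a positive signal would go unverified, or might belong to another compound of the same mass. Aim 1.2 uses dual chromatography and plans retention-time and MS/MS checks against authentic standards for significant metabolites, which is the case in question. The documents give no basis for a specific confusion of compounds, so no weight is put on it. What remains is that verification is discretionary and tied to significance.

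**Power.** The gap has no fixed size. It narrows with a looser FDR, denser signals or a larger effect: at 1.2 SD the three Step 2 thresholds give 0.81, 0.61 and 0.43. Mixed models on serial samples may do better than a single Wilcoxon test, though a candidate family could use the same models.

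**Other routes.** The metabolome-wide association study of specific metabolites does not name these candidates. The raw p<0.05 fallback applies when a comparison yields no FDR-significant metabolites, and feeds later and pathway analyses. Neither is a pre-specified individual test.

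**Stakes.** Aim 1 is exploratory, and the randomized primary endpoint is untouched.

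**Conclusion.** The point holds as a mismatch between the candidates the plan says it will test and those the targeted panel measures. Glycine, glutamine/glutamate and triacylglycerols are candidate-column entries that the panel omits. Sphingosine is not named, and 3-HIB is expected in section B but not assayed.

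At 25 v 25 and 1 SD, moving such a metabolite from a 2,000-feature screen to a five-member family at FDR 0.05 changes power from about 0.19–0.61 (20–200 true signals) to 0.77–0.87. At the preliminary-data density the screen gives 0.49. At FDR 0.20 the screen reaches 0.49–0.84, or 0.76 at the preliminary density, so with a lenient level and dense signals most of the loss disappears. These figures rest on the assumptions listed above; the preliminary density counts features called significant, not known true signals.

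The consequence is limited to interpretation, chiefly of null results for the named candidates in Aims 1 and 2.3. It is worth correcting because the change is cheap and, by the research timeline, laboratory assays begin only in year 4.

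**What to change.** In Aims 1.1 and 1.2 of section D1, and again for Aim 2.3:

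- Name 3-HIB, sphingosine, glycine, glutamine and glutamate as a small pre-specified candidate family, and say whether the glutamine/glutamate ratio is tested as its own member. Assign triacylglycerols explicitly to the panel or to the screen.
- Quantify the family from the planned high-resolution run by the reference standardization in Figure 7, or add it to the planned LC-MS/MS run.
- Confirm the identity of each member against an authentic standard whether or not it is significant.
- Correct within this family at a stated FDR level, separately from the untargeted screen, and state the FDR level for the screen as well.

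The cost is a few standards or some extra data processing, plus protocol wording, and a slightly larger candidate family to correct over. It needs no further patients or blood draws.
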